4.6.1 Exposure of Study Medication

Ocrelizumab exposure during the main treatment period will be summarized, including duration and dosage. The main treatment period is defined in Section 2. Accordingly, the duration is calculated as follows:

For patients who received Week 72 dose during the long term extension period, the duration of ocrelizumab exposure during the main treatment period = (Date prior to Week 72 dose – date of first dose) + 1

For patients who did not receive Week 72 dose, the duration = (the earlier of CCOD/completing/discontinuing treatment – date of first dose) +1

Ocrelizumab exposure during the long term extension treatment period will also be summarized for patients who received Week 72 dose, including duration and dosage. The long term extension treatment period is defined in Section 2.

Accordingly, the duration is calculated as (the earlier of CCOD/date of completing/discontinuing long term extension treatment – date of Week 72 dose) +1.

Ocrelizumab exposure for the entire study will be summarized and calculated as the (date of last dose - date of first dose) + 1.

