3. STUDY DESIGN

3.1 DESCRIPTION OF THE STUDY

This is an open-label, multicenter, biomarker study conducted at centers in multiple countries in which all eligible patients will be enrolled to a single treatment arm of ocrelizumab. *The study will include an RMS cohort and a PPMS cohort (see Table 1). The RMS cohort is the main cohort and will include the majority of study participants. The RMS cohort will be comprised of four arms, three of which will have patients randomized into one of three arms (Arms 1–3) depending on the time of their second lumbar puncture (LP). In Arm 4, treatment with ocrelizumab will be delayed for 12 weeks after the first LP. The PPMS cohort will comprise a smaller, hypothesis-generating portion of the trial, as less is known about PPMS biomarkers.*

Arm 4 will provide a control for Arm 1 of the RMS cohort. Due to the relapsing and remitting nature of RMS, some biomarkers may change due to disease course rather than based on influence of a drug treatment. Therefore, some biomarkers may “regress to the mean” across the disease course over time, and this change could then inaccurately be reported as a change due to drug treatment over time. Arm 4 will allow for an estimate of the natural variability of the disease when analyzing the other treated arms.

Male and female patients age 18–55 years with a diagnosis of RMS or PPMS in accordance with the 2010 revised McDonald criteria ([Polman et al. 2011; Appendix 7](#)) and an EDSS score of 0–5.5 points for RMS patients, or an EDSS score of 3.0–6.5 for PPMS patients, at screening will be eligible. Screening will occur over a 4-week period, after which eligible patients may begin treatment with ocrelizumab.

For patients in the RMS cohort (Arms 1–3), ocrelizumab will be administered at Week 1, Week 3, Week 24, and Week 48. The first dose will be administered as two infusions of 300 mg given on Day 1 and Day 15. The subsequent doses will be given as single 600-mg infusions.

For patients in the RMS cohort (Arm 4), after receiving two LPs at Week –12 and Week 1, the first dose of ocrelizumab will be administered as two 300-mg infusions on Week 1 (Day 1) and Week 3 (Day 15), with subsequent doses given as single 600-mg infusions at Weeks 24 and 48. The timeline for Arm 4 will continue for an extra 12 weeks to accommodate the same one-year dosing regimen.

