Ocrelizumab must not be administered as an IV push or bolus. Well-adjusted infusion pumps should be used to control the infusion rate, and ocrelizumab should be infused through a dedicated line. It is important not to use evacuated glass containers, which require vented administration sets, to prepare the infusion because this causes foaming as air bubbles pass through the solution.

After completion of the infusion, the IV cannula should remain in situ for at least 1 hour to allow for administration of drugs intravenously, if necessary, in the event of a delayed reaction. If no adverse events occur during this period of time, the IV cannula may be removed and the patient may be discharged.

See the Ocrelizumab Investigator's Brochure for detailed instructions on drug preparation, storage, and administration.

An overview of the ocrelizumab dosing is presented in [Table 2](#) and [Table 3](#).

Table 2 Overview of Ocrelizumab Dosing: RMS Cohort

	1 st Dose ^{a,c}		Subsequent Dose(s) ^{b,c}
	Day 1 Infusion	Day 15 Infusion	
Ocrelizumab	300 mg IV	300 mg IV	600 mg IV

IV=intravenous; RMS =relapsing multiple sclerosis.

Note: Before each infusion of ocrelizumab, 100 mg of methylprednisolone IV will be administered to reduce the potential for infusion-related reactions. Each treatment period has a duration of 24 weeks.

^a The first dosing will consist of two IV infusions separated by 14 days (i.e., Days 1 and 15).

^b Beginning with the second dose, a single infusion of ocrelizumab will be administered.

^c Prior to the next infusion, a clinical evaluation will be performed to ensure that the patient remains eligible for retreatment.

Table 3 Overview of Ocrelizumab Dosing: PPMS Cohort

Group	1 st Dose ^a		Subsequent Dose(s) ^a	
	Day 1 Infusion	Day 15 Infusion	First Infusion	Next Infusion (14 days later)
Ocrelizumab	300 mg IV	300 mg IV	300 mg IV	300 mg IV

IV =intravenous; PPMS =primary progressive multiple sclerosis.

Note: Before each infusion of ocrelizumab, 100 mg of methylprednisolone IV (or equivalent IV steroid) will be administered to reduce the potential for infusion-related reactions. Each treatment period has a duration of 24 weeks.

^a Prior to the next infusion, a clinical evaluation will be performed to ensure that the patient remains eligible for retreatment.

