2. STUDY DESIGN

This is an open-label, multicenter, biomarker study conducted at centers in multiple countries in which all eligible patients will be enrolled to a single treatment arm of ocrelizumab. The study will include an RMS cohort and a PPMS cohort. The RMS cohort is the main cohort and will include the majority of study participants. The RMS cohort will be comprised of four arms, three of which will have patients randomized into one of three arms (Arms 1-3) depending on the time of their second lumbar puncture (LP). In Arm 4, treatment with ocrelizumab will be delayed for 12 weeks after the first LP. The PPMS cohort will comprise a hypothesis-generating portion of the trial, as less is known about PPMS biomarkers.

The study treatment period is comprised of a Main Treatment Period and a Long-term Extension Period. For patients who complete the Main Treatment Period and continue to receive ocrelizumab, a Long-term Extension Period of the study will begin at Week 72 and administer ocrelizumab every 6 months for up to 4 years. The main treatment period will end on the earlier of the dates in which that patient received the Week 72 dose and the date in which Week 72 lab data were collected, or to data cutoff date or end of study date if patient hasn't received the week 72 dose. The long term extension period for each patient will start from the earliest day that patient takes the Week 72 dose or Week 72 lab data is collected till data cutoff date or end of study.

During the Main Treatment Period of the study, two LPs will be drawn from each patient. The two LPs will allow for assessment of biomarkers in CSF that are indicative of response to drug, pharmacokinetic/pharmacodynamic relationships, and/or disease pathogenesis in the CNS. Optional LPs may be collected upon patient's additional consent. Specifically:

Patients in the RMS cohort (Arms 1-3) will receive an LP before the start of dosing with ocrelizumab. Subsequently, these patients will be randomized into one of three arms for timing of the second LP, either Week 12, 24, or 52 following the first dose of ocrelizumab.

Patients in Arm 4 will receive two LPs, separated by a 12-week interval, before administration of the first dose of ocrelizumab. Patients in this arm will be asked if they are willing to give optional CSF samples via LP 12 weeks and 52 weeks after the ocrelizumab dose.

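### Whole-study ocrelizumab exposure stops at the last infusion, while main-period and extension exposure run to a later end date, so the parts can exceed the whole

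*SAP*

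**What the plan says.** SAP section 4.6.1 defines three exposure durations.

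- **Main period, Week 72 dose received:** from the first dose to the day before the Week 72 dose, counting both days.
- **Main period, Week 72 dose not received:** "For patients who did not receive Week 72 dose, the duration = (the earlier of CCOD/completing/discontinuing treatment – date of first dose) +1".
- **Long-term extension (LTE):** "the duration is calculated as (the earlier of CCOD/date of completing/discontinuing long term extension treatment – date of Week 72 dose) +1".
- **Whole study:** "Ocrelizumab exposure for the entire study will be summarized and calculated as the (date of last dose - date of first dose) + 1".

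The first three run to an end of treatment, a data cutoff, or the start of the next period. The fourth runs to an infusion date. No reason is given for the difference.

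Protocol section 3.1 gives the RMS schedule (Arms 1–3): "ocrelizumab will be administered at Week 1, Week 3, Week 24, and Week 48". The notes to the protocol's dosing tables (section 4.3.2.1) add: "Each treatment period has a duration of 24 weeks". SAP section 2 describes the extension: "Long-term Extension Period of the study will begin at Week 72 and administer ocrelizumab every 6 months for up to 4 years". SAP section 2.2.5 lists exposure, including duration, as a safety outcome measure, and SAP Table 2 includes exposure in all four analyses it covers.

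**The concern.** The main period and the extension together make up the study treatment period, so a reader expects their exposures to add to the whole-study figure. As written they do not whenever time passes between the last infusion and the end date. In a patient who never received the Week 72 dose, the whole can even be shorter than its only part.

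The drug is given at long intervals, so the gap is not trivial. The main-period rule credits an extension entrant with the interval after the Week 48 dose, up to the day before Week 72. The whole-study rule credits the final dose with a single day.

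At stake is the internal consistency of a listed safety outcome measure. A clinical study report giving both durations would show totals that do not reconcile, without an explanation in the plan.

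**Working it through.** The documents state no exposure figure to reproduce, so the check applies the SAP formulas to nominal study days.

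**Inputs.** First dose = Day 1. RMS doses at Day 168 (Week 24) and Day 336 (Week 48), and the Week 52 visit at Day 364, come from protocol Appendix 1. The last main-period PPMS infusion at Day 350 (Week 50) comes from protocol Appendix 3. Week 72 = Day 504, Week 216 = Day 1,512 and Week 240 = Day 1,680 come from SAP Appendix 2. One treatment period = 24 × 7 = 168 days. End dates marked * are assumptions for illustration.

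**Formulas.**
- Main, no Week 72 dose = end − first + 1
- Main, Week 72 dose = (W72 − 1) − first + 1 = W72 − first
- LTE = end − W72 + 1
- Whole = last dose − first + 1

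**Patients without a Week 72 dose.**

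| Case | Main (days) | Whole (days) | Shortfall |
|---|---|---|---|
| RMS, last dose D336, ends D364 | 364 | 336 | 28 |
| PPMS, last infusion D350, ends D364 | 364 | 350 | 14 |
| One infusion, discontinues D84* | 84 | 1 | 83 |
| Infusions D1 and D15, discontinues D168* | 168 | 15 | 153 |
| Last dose D168, cutoff at D300* | 300 | 168 | 132 |
| Last dose D336, end recorded as D336* | 336 | 336 | 0 |

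**Patients with a Week 72 dose at Day 504** (main = 504 − 1 = 503 days).

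| Case | Main + LTE (days) | Whole (days) | Shortfall |
|---|---|---|---|
| Last dose D504, ends D600* | 503 + 97 = 600 | 504 | 96 |
| Last dose D1,512, ends D1,680* | 503 + 1,177 = 1,680 | 1,512 | 168 |
| Last dose D1,680, ends D1,680* | 503 + 1,177 = 1,680 | 1,680 | 0 |
| Last dose D1,680, ends D1,848* | 503 + 1,345 = 1,848 | 1,680 | 168 |

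In both groups the shortfall is exactly end date − last dose date. In extension patients the whole is at least 504 days and main is 503, so the whole never falls below main; it falls below main plus LTE.

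**With a common end date.** Main + LTE = (W72 − first) + (end − W72 + 1) = end − first + 1. A whole-study definition of end − first + 1 therefore equals the sum for every extension patient, and equals main-period exposure for everyone else.

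**The case against.** The best defence is that the completion or discontinuation date may be recorded as the last infusion date. The formulas then agree, apart from patients censored at a cutoff. SAP section 4.2 mentions a CRF for completing or discontinuing ocrelizumab but does not say what date it holds, so this cannot be excluded. The text leans the other way: without a Week 72 dose, SAP section 2 ends the main period at the data cutoff or end of study, and 4.6.1 says its durations follow from that definition. Even under this convention, two patients with identical dosing through Week 48 would have main-period exposures of 503 days (extension entrant) and 336 days (non-entrant).

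It can also be said that first-to-last-dose time is a legitimate description of dosing duration, and that the 24-week statement describes the schedule rather than how exposure is derived. Both are fair. They support reporting that quantity under its own name, not giving the same name to a quantity with a different end point.

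The extension examples with a 168-day loss are not established by the plan either. The SAP's synopsis (Appendix 1) ties extension assessments to infusions and puts treatment at about 4.5 years, or 4.5 × 365.25 / 7 ≈ 235 weeks. A last infusion and completion both at Week 240 would give no loss.

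Finally, the Final Analysis is limited to main-period data (SAP section 4.9), so the whole-study figure may appear only at the LTE Final Analysis, when few patients should still be censored at a cutoff. Section 4.6.1 does not say where it will be used.

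**Conclusion.** The definitions in SAP section 4.6.1 are inconsistent as written and should be aligned. The shortfall per patient is the time from the last infusion to the end date: 28 days for an RMS patient and 14 for a PPMS patient ending at the Week 52 visit, zero if the end date is recorded as the last infusion, and potentially 168 days or more otherwise. The larger figures rest on assumed end dates.

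Four stronger readings are tempting, but the documents do not support them.

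- **Adverse event rates will be too high.** The SAP plans patient numbers, percentages and event counts. Protocol section 6.5 mentions incidence rates but names no person-time denominator. The harm arises only if an exposure-adjusted rate is computed later with this figure. Aligning the end date would not by itself supply a matched at-risk period, because adverse events are collected for 48 weeks after the last dose.
- **The study loses about 48 to 60 patient-years.** That is 104 × 168 / 365.25 = 47.8 to 130 × 168 / 365.25 = 59.8, and assumes that every patient loses a full interval. Nothing in the plan says so.
- **Early discontinuers are worst affected.** This is true proportionally (83 of 84 days in the one-infusion case), but not in absolute days, where other cases above lose 132 to 168.
- **The whole is always below main-period exposure, in a headline table.** It can be below only without a Week 72 dose. The output list is in a separate SAP module, so the table layout and prominence are unknown.

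The primary endpoints, analysis populations and study decisions are not affected.

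**What to change.** In SAP section 4.6.1:

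1. Define whole-study exposure as (earlier of CCOD and the date of completing or discontinuing treatment, including extension treatment − date of first dose) + 1. It then equals main plus LTE.
2. State how the completion or discontinuation date is defined, in particular whether it is the last infusion date, the end of the last dosing interval, or the date of the decision or visit.
3. If first-to-last-dose time is also wanted, report it separately, labelled as dosing duration.

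The cost is a sentence or two of SAP text and one changed derivation. No new data are needed if the end date is already on the CRF.

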4.6.2 Adverse Events

Treatment emergent adverse events and serious treatment emergent adverse events will be coded, summarized overall and by NCI CTCAE v4.0 grade, and tabulated by body system and Preferred Term for individual events within each body system.

The number and percentage of patients with at least one IRR, and the intensity (highest grade for each patient) will be summarized in total and by dose cycle (patients with multiple events within an infusion will count only once). In addition, the total number of IRRs will be summarized (multiple events will be counted) in total and by dose cycle.

4.6.3 Laboratory Data

Subject listing of abnormalities in selected safety labs will be provided if needed.

4.6.4 Anti-drug Antibodies (ADAs)

The number and percentage of patients that developed ADAs will be summarized.

4.6.5 Adverse Event of Special Interest (AESI)

All reported AESI will be summarized overall and by NCI CTCAE v4.0 grade, and tabulated by specific MedDRA bucket terms and preferred terms. The following types of events are of special interest:

- Drug-induced liver injury
- Suspected transmission of an infectious agent via product

4.6.6 Vital Signs

Vital signs and physical examination results will be presented in patient listings if deemed necessary.

4.7 MISSING DATA

Missing data will not be imputed for efficacy analyses. For partial dates used for summaries such as treatment emergent adverse events, refer to the DAP module 3 for imputation of partial dates.

4.8 INTERIM ANALYSES

Given the hypothesis-generating nature and publication intent of this study, several interim analyses are planned as listed in Table 1, Section 2.4 and no formal multiplicity adjustment is necessary. The interim analyses will be performed and interpreted by members of the Sponsor study team and appropriate senior management personnel. No decision will be made on study conduct based on the interim analyses.

4.9 SCOPE OF PLANNED ANALYSES

Interim Analysis 1 was limited to patients in the RMS cohorts Arms 1-3 who were enrolled by the CCOD. Biomarker analyses were limited to the Biomarker Population.

Interim Analysis 2 will be limited to patients in the RMS cohort Arms 1-4. Only data during the Main Treatment Period (defined in Section 2, before receiving Week 72 treatment) will be summarized at this interim analysis, which applies to patient disposition information, efficacy endpoints and safety endpoints.

The Final Analysis will include all patients (RMS cohort Arms 1-4 and PPMS cohort). Only data during the Main Treatment Period will be summarized.

The LTE Final Study Analysis will include all patients and all data collected during the Long Term Extension Period and the Safety Follow Up period.

The endpoints that will be included in each of the analyses and the analysis populations are specified in Table 2. Specific list of planned outputs will be available in SAP Module 2.

Table 2 Scope of Planned Analyses

Endpoint	Interim Analysis 1	Interim Analysis 2	Final Analysis	LTE Final Analysis
Disposition & Baseline Demographics, characteristics	X (RMS Enrolled Population, Biomarker Population)	X (RMS Enrolled Population)	X (Enrolled Population)	X (Enrolled Population)
Efficacy Endpoints (depend on data availability)	X (RMS Biomarker Population)	X Selected biomarkers as specified in SAP Module 2. (RMS Enrolled Population)	X (Enrolled Population, Per-Protocol Population)	X (Enrolled Population, Per-Protocol Population)
Pharmacokinetic (depend on data availability)	Not Planned	Depend on data availability	X (Pharmacokinetic Evaluable Population)	X (Pharmacokinetic Evaluable Population)
Exposure, AE, IRR	X (RMS Safety Population)	X (RMS Safety Population)	X (Safety Population)	X (Safety Population)
ADA	Not Planned	Not Planned	X (Safety Population)	X (Safety Population)
Vital Signs and General Laboratory Data	Not Planned	Not Planned	X (Safety Population)	X (Safety Population)

APPENDIX 1 PROTOCOL SYNOPSIS

TITLE: AN OPEN-LABEL, MULTICENTER, BIOMARKER STUDY TO EXPLORE THE MECHANISM OF ACTION OF OCRELIZUMAB AND B-CELL BIOLOGY IN PATIENTS WITH RELAPSING MULTIPLE SCLEROSIS OR PRIMARY PROGRESSIVE MULTIPLE SCLEROSIS

PROTOCOL NUMBER: ML29966

VERSION NUMBER: 5 (U.S.)

EUDRACT NUMBER: 2015-004616-37

IND NUMBER: 100,593

TEST PRODUCT: Ocrelizumab (RO4964913)

PHASE: IIIb

INDICATION: Relapsing multiple sclerosis and primary progressive multiple sclerosis

SPONSOR: Genentech, Inc.

Objectives and Endpoints

This is an exploratory biomarker study designed to be hypothesis-generating in order to better understand the mechanism of action of ocrelizumab and B-cell biology in relapsing multiple sclerosis (RMS) and primary progressive multiple sclerosis (PPMS).

Primary Objectives

The primary objectives for the RMS cohort in this study are:

- To understand the impact of ocrelizumab treatment on neurofilament light (NFL) as a biomarker of neuronal damage in cerebrospinal fluid (CSF)
- To assess the number of CD19+ B cells in CSF (cell number/microliter) before and after treatment with ocrelizumab
- To assess the number of CD3+ T cells in CSF (cell number/microliter) before and after treatment with ocrelizumab

Exploratory Objectives

The exploratory objectives for the PPMS cohort in this study are:

- To understand the impact of ocrelizumab treatment on NFL as a biomarker of neuronal damage in CSF
- To assess the number of CD19+ B cells in CSF (cell number/microliter) before and after treatment with ocrelizumab
- To assess the number of CD3+ T cells in CSF (cell number/microliter) before and after treatment with ocrelizumab

The exploratory objectives for both cohorts in this study are:

- To understand the impact of ocrelizumab treatment on NFL and other biomarkers of neurodegeneration in CSF as a reflection of activity in the central nervous system (CNS) and compared with peripheral blood

- To measure the impact of ocrelizumab treatment on B cells/B-cell subsets, T cells/T-cell subsets, and other cell types (e.g., natural killer cells, monocytes, etc.), functional parameters of B/T/other cell types (activation, cell products), and other biomarkers of inflammation in CSF as a reflection of activity in the CNS and compared with peripheral blood
- To assess potential correlation between change in blood or CSF biomarkers of neurodegeneration or inflammation and change in magnetic resonance imaging (MRI) or efficacy outcome measures, such as reduction in gadolinium (Gd)-positive lesions or Expanded Disability Status Scale (EDSS) score

The exploratory objectives for the Long-Term Extension are:

- *To understand the impact of ocrelizumab on indices of neurodegeneration*
- *To monitor the clinical condition of the patient over an extended period of time*

Exploratory objectives for the RMS delayed time to start control arm (Arm 4) will include comparisons between Arm 1 of the RMS cohort (second lumbar puncture [LP] at 12 weeks) and Arm 4 (*first* LP at 12 weeks before the first dose of study drug), and may include but not be limited to changes in CSF, blood, and MRI biomarkers or efficacy, as outlined above.

Pharmacokinetic Objective

The pharmacokinetic objective for this study is:

- To assess pharmacokinetics of ocrelizumab in CSF compared with serum concentration

Immunogenicity Objective

The immunogenicity objective for this study is:

- To assess the incidence of anti-drug antibodies to ocrelizumab

Safety Objectives

The safety objective for this study, *including for the Long-Term Extension*, is to evaluate the safety of ocrelizumab on the basis of the following endpoints:

- Nature, frequency, severity, and timing of adverse events
- Changes in vital signs, physical findings, and clinical laboratory results during and following ocrelizumab administration
- Adverse events related to biomarker sample collection

Study Design

Description of Study

This is an open-label, multicenter, biomarker study conducted at centers in multiple countries in which all eligible patients will be enrolled to a single treatment arm of ocrelizumab. The study will include an RMS cohort and a PPMS cohort (see Table 1). The RMS cohort is the main cohort and will include the majority of study participants. The RMS cohort will be comprised of four arms, three of which will have patients randomized into one of three arms (Arms 1–3) depending on the time of their second LP. In Arm 4, treatment with ocrelizumab will be delayed for 12 weeks after the first LP. The PPMS cohort will comprise a smaller, hypothesis-generating portion of the trial, as less is known about PPMS biomarkers.

Arm 4 will provide a control for Arm 1 of the RMS cohort. Due to the relapsing and remitting nature of RMS, some biomarkers may change due to disease course rather than based on influence of a drug treatment. Therefore, some biomarkers may “regress to the mean” across the disease course over time, and this change could then inaccurately be reported as a change due to drug treatment over time. Arm 4 will allow for an estimate of the natural variability of the disease when analyzing the other treated arms.

Male and female patients age 18–55 years with a diagnosis of RMS or PPMS in accordance with the 2010 revised McDonald criteria (Polman et al. 2011; Appendix 7) and an EDSS score of 0–5.5 points for RMS patients, or an EDSS score of 3.0–6.5 for PPMS patients, at screening will be eligible. Screening will occur over a 4-week period, after which eligible patients may begin treatment with ocrelizumab.

For patients in the RMS cohort (Arms 1–3; *see Appendix 1*), ocrelizumab will be administered at Week 1, Week 3, Week 24, and Week 48 (*and every 24 weeks beginning at Week 72 per the*

Long-Term Extension; see Appendix 9). The first dose will be administered as two infusions of 300 mg given on Day 1 and Day 15. The subsequent doses will be given as single 600-mg infusions.

For patients in the RMS cohort (Arm 4; *see Appendix 2*), after receiving two LPs at Week -12 and Week 1, the first dose of ocrelizumab will be administered as two 300-mg infusions on Week 1 (Day 1) and Week 3 (Day 15), with subsequent doses given as single 600-mg infusions at Weeks 24 and 48 (*and every 24 weeks beginning at Week 72 per the Long-Term Extension; see Appendix 9*). The timeline for Arm 4 will continue for an extra 12 weeks to accommodate the same one-year dosing regimen.

For patients in the PPMS cohort (*see Appendix 3*), ocrelizumab 600 mg will be administered as two 300-mg IV infusions separated by 14 days at a scheduled interval of every 24 weeks (*and every 24 weeks as a single dose beginning at Week 72 per the Long-Term Extension; see Appendix 9*).

Treatment with ocrelizumab will continue for approximately 4.5 years after the first infusion; however, treatment may be stopped at any time due to lack of clinical benefit, unacceptable toxicity, withdrawal of consent, patient or physician decision to discontinue treatment, death, or if the Sponsor decides to close the trial, whichever occurs first.

Patients who complete the study and choose not to continue on ocrelizumab treatment, or who discontinue from treatment early, should enter the Safety Follow-up Period and be assessed every 24 weeks for 48 weeks counting from the date of the last infusion of ocrelizumab. After 48 weeks, if the peripheral blood B-cell count remains depleted, monitoring of the patient should continue at 24-week intervals until the B-cell count has returned to the baseline value or to the lower limit of the normal range, whichever is lower (see Appendix 8).

For patients who complete the study and continue to receive ocrelizumab, a Long-Term Extension of the study beginning at Week 72 will be conducted every 6 months for up to 4 years at the time of treatment infusion for as long as they continue to receive ocrelizumab (Appendix 9). A Long-Term Extension of the study is needed to understand the correlation between long-term changes in biomarker assessments with long-term safety and long-term efficacy of ocrelizumab. The Long-Term Extension extends the study to a total of 5 years, which is the necessary timeframe to investigate whether baseline CSF NfL levels may be prognostic for long-term brain atrophy as assessed by 5-year declines in whole brain volume in MS patients (Arrambide et al. 2016). CSF NfL and serum NfL levels are highly correlated in the disease (Disanto et al. 2017), and therefore measurement of blood NfL levels may allow for predictions of brain atrophy in MS patients. Treatment of MS patients with disease-modifying therapies has been demonstrated to cause short-term (6 months to 1 year) accelerations in whole brain-volume loss (pseudoatrophy) but slows long-term (3 – 5 years) brain atrophy (Zivadinov et al. 2008). Therefore, a Long-Term Extension is needed in order to accurately establish an association between serum NfL levels and brain atrophy in patients in the study.

Biomarkers will be monitored in a longitudinal fashion before and after treatment with ocrelizumab in order to assess dynamic changes in biomarkers as they relate to drug exposure, length of time on drug, response to drug, and MS disease pathogenesis. Biomarkers will be assessed via blood draws throughout the study and via LP in CSF at baseline before the first dose of ocrelizumab and at one other timepoint.

Two LPs will be drawn from each patient during the study (*except in the case of consent for optional LPs*). The two LPs will allow for assessment of biomarkers in CSF that are indicative of response to drug, pharmacokinetic/pharmacodynamic relationships, and/or disease pathogenesis in the CNS.

Patients in the RMS cohort (Arms 1–3) will receive an LP before the start of dosing with ocrelizumab. Subsequently, these patients will be randomized into one of three arms for timing of the second LP, either Week 12, 24, or 52 following the first dose of ocrelizumab.

Patients in Arm 4 will receive two LPs, separated by a 12-week interval, before administration of the first dose of ocrelizumab. Patients in this arm will be asked if they are willing to give an optional CSF sample via LP 12 weeks after the ocrelizumab dose.

Patients in the PPMS cohort will receive an LP at the start of the study before dosing with ocrelizumab. Subsequently, they will receive a second LP at Week 52 following the first dose of ocrelizumab.

In the case of MS relapse or worsening (for PPMS patients) during the study, the patient should have an unscheduled visit and will be asked to receive an optional LP at the time of relapse or worsening (for PPMS patients). The patient will have another LP at the originally scheduled time based on their randomization, or if a relapse occurs after they have already given the second LP, the relapse LP will remain optional. *Patients in Arms 1, 2, and 4 will also be asked to have an additional, optional LP at Week 52.*

Patients will be asked to consent to LPs during the Long-Term Extension.

All patients will be evaluated for safety throughout the study.

In the case of early termination, the patient will be asked to have an early termination visit.

Number of Patients

Approximately 120 patients will be enrolled in this study; 88 patients with RMS and up to 32 patients with PPMS.

Target Population

Inclusion Criteria

General Inclusion Criteria

Patients must meet the following criteria for study entry:

- Signed Informed Consent Form
- Ability to comply with the protocol, in the investigator's judgment
- Age 18–55 years, inclusive
- For women of childbearing potential: agreement to remain abstinent (refrain from heterosexual intercourse) or use contraceptive methods that result in a failure rate of <1% per year during the treatment period and for at least 24 weeks after the last dose of study treatment or until their B cells have repleted, whichever is longer
 - A woman is considered to be of childbearing potential if she is postmenarcheal, has not reached a postmenopausal state (≥ 12 continuous months of amenorrhea with no identified cause other than menopause), and has not undergone surgical sterilization (removal of ovaries and/or uterus).
 - Examples of contraceptive methods with a failure rate of <1% per year include bilateral tubal ligation, male sterilization, established, proper use of hormonal contraceptives that inhibit ovulation, hormone-releasing intrauterine devices, and copper intrauterine devices.
 - The reliability of sexual abstinence should be evaluated in relation to the duration of the clinical trial and the preferred and usual lifestyle of the patient. Periodic abstinence (e.g., calendar, ovulation, symptothermal, or postovulation methods) and withdrawal are not acceptable methods of contraception.

Inclusion Criteria Specific to RMS Patients

- Diagnosis of RMS in accordance with the 2010 revised McDonald criteria (Polman et al. 2011; Appendix 7)
- EDSS score of 0–5.5 points, inclusive, at screening
- Disease duration from the onset of MS symptoms:
 - Less than 15 years in patients with an EDSS >5.0 at screening
- Either treatment-naïve or receiving treatment with disease-modifying therapies, including prior use of interferon (IFN)- β -1a (Avonex $^{\circledR}$, Rebif $^{\circledR}$), IFN- β -1b (Betaseron $^{\circledR}$ /Betaferon), or glatiramer acetate (Copaxone $^{\circledR}$)
- At least one clinically documented relapse in the past year and/or at least one T1-weighted Gd-enhancing lesion in the past year and/or at least one new T2 lesion in the past year at the time of enrollment

Inclusion Criteria Specific to RMS Cohort Arm 4

- Must meet inclusion criteria for the RMS cohort
- Separate signed Informed Consent Form for the RMS Delayed Time to Start Control Arm (Arm 4)
- Must be willing to remain on the same dose and regimen of current standard of care, or no treatment if treatment-naïve, for 12 weeks after study enrollment
 - The treating and/or study physician must agree that the patient is eligible to remain on the same dose and regimen of their current standard of care at screening, or to receive no treatment if the patient is treatment-naïve, for 12 weeks after study enrollment.

Inclusion Criteria Specific to PPMS Patients

- Diagnosis of PPMS in accordance with the 2010 revised McDonald criteria (Polman et al. 2011; Appendix 7)
- EDSS score of 3.0–6.5 points, inclusive, at screening
- Disease duration from the onset of MS symptoms:
 - Less than 10 years in patients with an EDSS at screening \leq 5.0
- Documented history of at least one of the following laboratory findings in CSF:
 - Elevated IgG Index
 - One or more IgG oligoclonal bands detected by isoelectric focusing

Exclusion Criteria

General Inclusion Criteria

Patients who meet any of the following criteria will be excluded from study entry:

- Diagnosis of secondary progressive MS without relapses for at least 1 year
- History or known presence of recurrent or chronic infection (e.g., HIV, syphilis, tuberculosis)
- History of recurrent aspiration pneumonia requiring antibiotic therapy
- History of cancer, including solid tumors and hematological malignancies (except basal cell, in situ squamous cell carcinomas of the skin, and in situ carcinoma of the cervix or the uterus that have been excised and resolved with documented clean margins on pathology)
- History of or currently active primary or secondary immunodeficiency
- History of coagulation disorders
- History of severe allergic or anaphylactic reactions to humanized or murine monoclonal antibodies
- History of alcohol or other drug abuse within 24 weeks prior to enrollment
- Known presence or history of other neurologic disorders, including but not limited to, the following:
 - History or known presence of progressive multifocal leukoencephalopathy
 - History or known presence of CNS or spinal cord tumor (e.g., meningioma, glioma)
 - History or known presence of potential metabolic causes of myelopathy (e.g., untreated vitamin B12 deficiency)
 - History or known presence of infectious causes of myelopathy (e.g., syphilis, Lyme disease, HTLV-1, herpes zoster myelopathy)
 - History of genetically inherited progressive CNS degenerative disorder (e.g., hereditary paraparesis; mitochondrial encephalopathy, lactic acidosis, and stroke-like episodes [MELAS])
 - History or known presence of systemic autoimmune disorders, potentially causing progressive neurologic disease (e.g., lupus, anti-phospholipid antibody syndrome, Sjögren's syndrome, Behcet's disease)
 - History or known presence of sarcoidosis
 - Neuromyelitis optica

- Ischemic cerebrovascular disorders (e.g., stroke, transient ischemic attack) or ischemia of the spinal cord
 - Severe, clinically significant brain or spinal cord trauma (e.g., cerebral contusion, spinal cord compression)
- Significant, uncontrolled disease, such as cardiovascular (including cardiac arrhythmia), pulmonary (including chronic obstructive pulmonary disease), renal, hepatic, endocrine, gastrointestinal, or any other significant disease
- Congestive heart failure (according to New York Heart Association III or IV functional severity)
- Known active bacterial, viral, fungal, mycobacterial infection, or other infection (including tuberculosis or atypical mycobacterial disease, but excluding fungal infection of nail beds) or any major episode of infection requiring hospitalization or treatment with IV antibiotics within 4 weeks prior to baseline visit or oral antibiotics within 2 weeks prior to baseline visit
- Any concomitant disease that may require chronic treatment with systemic corticosteroids or immunosuppressants during the course of the study
- Contraindications for, or intolerance to, oral or IV corticosteroids, including IV methylprednisolone, according to the country label, including:
 - Psychosis not yet controlled by a treatment
 - Hypersensitivity to any of the treatment drug constituents
- Contraindication for LP
- Previous treatment with B cell-targeted therapies (e.g., rituximab, ocrelizumab, atacicept, belimumab, or ofatumumab)
- Previous treatment with natalizumab (Tysabri®), alemtuzumab, anti-CD4 agents, cladribine, teriflunomide, cyclophosphamide, mitoxantrone, azathioprine, mycophenolate mofetil, cyclosporine, methotrexate, total body irradiation, or bone marrow transplantation
- Treatment with fingolimod (Gilenya®), dimethyl fumarate (Tecfidera®), or similar treatment within 6 months prior to enrollment
- Receipt of a live vaccine within 6 weeks prior to enrollment
 - **Vaccinations before baseline:** In rare cases where a live vaccine must be administered by the patient's physician, the screening period may need to be prolonged but cannot exceed 12 weeks.
- Systemic corticosteroid therapy within 4 weeks prior to baseline
